### **6.9.1.2 OLE Phase**

Octreotide capsules can be up-titrated or down titrated during the OLE. All patients will start on 60 mg/day and can either down titrate to 40 mg/day or up titrate to 80 mg/day, based on clinical and biochemical response.

In the OLE, the duration of study drug exposure (in days) will be summarized by the treatment group and overall, using descriptive statistics. Duration of study drug exposure will be calculated as date of last dose in the OLE– date of first dose in the OLE + 1.

The number and proportion of patients at each dose level (40, 60 and 80 mg/day) at the end of the OLE, will also be presented by treatment group and overall.

Compliance to each dose level of octreotide capsules from first dose in the OLE through the last visit of the OLE will be calculated and summarized by treatment group and overall, and also by the final target dose level achieved within each treatment group during the OLE.

For the purpose of analysis, compliance to each dose level during the OLE will be calculated as  $100 \times (\text{total number of capsules actually taken} / \text{total number of capsules expected to be taken})$ . This calculation will be used for each dose level the patient received during the OLE. The numbers and percentages of patients <75% compliant, 75-100% compliant, and >100% compliant will be tabulated.

The number of actual capsules taken for each dose level will be the total number of capsules dispensed – total number of capsules returned during the time the patient was on that particular dose.

The number of expected capsules taken for the target dose level will be derived as follows:

Dose Level	Expected Number of Capsules Taken
40 mg	2 capsules × (first day of the phase – last day of the phase)
60 mg	3 capsules × (first day of the phase – last day of the phase)
80 mg	4 capsules × (first day of the phase – last day of the phase)
Overall	Sum of expected number of capsules taken over all of the dose levels assigned

## 6.9.2 Adverse Events

Adverse events will be coded using MedDRA (version 18.1 or higher).

### 6.9.2.1 DPC period

All AEs that occur after randomization (i.e., date of onset is on or after the date of randomization) and on or before the end of treatment (last dose of blinded study drug) in the DPC period will be considered Treatment Emergent Adverse Events (TEAEs) for the purpose of reporting in the DPC period, and will be summarized using frequency counts and percentages. Summaries will be presented by final dose group and treatment group (i.e., octreotide 40, 60, 80, overall and placebo) and overall for the safety set.

If the day of onset of an AE is missing, then if the month and year of an onset date are on or after the date of randomization, the following rules will be applied:

- If month/year of the onset date is on or after the month/year of randomization, the AE will be considered treatment emergent;
- If month/year of the onset date is equal to the month/year of randomization, and the end date is present, the end date will be used to determine when the AE started. If the end date is on or after randomization, the AE will be considered treatment emergent; otherwise, if the AE stopped before randomization, then it will not be considered treatment emergent;
- If month/year of the onset date is equal to the month/year of randomization, and the end date is a partial date, the AE will be considered treatment emergent;
- If, despite implementing the above conventions, the onset date of the AE cannot be placed before, on, or after randomization, then the event will be considered treatment emergent.

Summaries of TEAEs will be presented using the MedDRA level hierarchy (system organ class, high level group term, high level term, and preferred term) as follows:

- Overall (i.e., regardless of intensity or relationship to treatment)
- By intensity grade (mild, moderate, severe)
- By relationship to study medication (potential relationship to study treatment or unlikely/no relationship to study treatment) according to the mapping scheme below:
  - Related: will include all AEs with a relationship rating of “related” or “possibly related”
  - Not related: will include all AEs with a relationship rating of “Not related”
- Unless otherwise specified, at each level of patient summarization in reporting the incidence of the AEs, a subject will be counted once if the subject reported one or more events. If more than one occurrence of an event is reported, the event of the worst intensity or the worst-case relationship assessment will be summarized.

TEAEs leading to premature discontinuation of study drug and serious TEAEs (SAEs) will also be summarized by treatment group and relationship. TEAEs leading to premature discontinuation of study drug will be defined as any TEAEs with an action taken regarding study medication equal to “permanently discontinued.”

Summaries of TEAEs overall, by relationship, leading to premature discontinuation and serious TEAEs will also be presented by sub-groups (region, age, gender and race) using descriptive statistics.

Summaries of AESI will be presented by intensity grade both overall and by individual AESI. The following are the AESIs which will be reported: headache, fatigue, perspiration, soft tissue swelling, arthralgia, dysglycemia, and hypertension. Additional AEs identified by the investigator may also be included as AESIs. In addition, summaries, will also be presented for AESIs leading to premature discontinuation of study drug, by severity. Unless otherwise specified, at each level of patient summarization in reporting the incidence of the AESIs, a subject will be counted once if the subject reported one or more events. If more than one occurrence of an event is reported, the event of the worst intensity will be summarized. An overall summary of the number and proportion of patients reporting 0, 1, 2, 3 and >3 AESIs will also be provided.

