### 2.2.2 Safety Outcomes

- Incidence of adverse events (AEs)
- Incidence of new or worsening adverse events of special interest (AESI)
- Absolute and change from baseline to each study visit in blood chemistry parameters
- Absolute and change from baseline to each study visit in blood hematology parameters
- Absolute and change from baseline to each study visit for Vital Signs (heart rate, blood pressure, body weight) and 12-lead ECG (PR, QRS, QTcF, heart rate)
- Incidence of clinically significant findings on abdominal ultrasound

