### 5.2.1 Baseline Visit

[REDACTED]

Patients meeting the eligibility criteria will be randomized at Baseline in 1:1 ratio to one of two treatment arms:

1. Octreotide capsules
2. Matching placebo capsules

[REDACTED]

The following assessments and procedures will be performed at Baseline (BL) Visit:

- Inclusion and exclusion criteria review and confirmation
- Vital signs
- Weight
- Safety laboratory tests: hematology, biochemistry, TSH, free T4, and lipid profile (total cholesterol, triglycerides, high-density lipoprotein, and low-density

 Low dose - octreotide dose 10 mg /month or lanreotide 60 mg /month or lanreotide 120 mg/8 weeks

 Time from last dose should not exceed injection interval +3 days

lipoprotein)

- Urine pregnancy test for women of childbearing potential, Positive urine pregnancy test will be followed by a confirmatory serum pregnancy test. In case of positive urine pregnancy test subjects could not be dosed, until the results of the serum pregnancy test will be available. Positive serum pregnancy test will result in a subject being a screening failure.
- IGF-1
- GH: Five samples every  $30 \pm 5$  minutes over two hours from time 0 to 2 hours
- Acromegaly directed and treatment directed physical examination
- Concomitant medications and AE recording
- Randomization and dispense study medication (call IVRS/IWRS)
- Study medication administration at the site (first dose, after the collection of blood samples for GH)
- Drug administration instructions:
  - apply food habits questionnaire, and adjust study medication administration and timing to the patient habits. Instruct the patient how he/she should take his/her other concomitant drugs (thyroid hormones, anti-diabetic medications, PPIs or H2 blockers).
  - Instruct the patient that study medications should be taken on an empty stomach at least one hour prior to a meal or at least two hours after. Optional drug administration timing for patients:

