AEs will be assessed at all study visits throughout the study from informed consent signing. AEs reported prior to dosing on Baseline Day will be captured and considered non-treatment emergent AEs. Treatment Emergent AEs (TEAEs) will be considered all AEs that occurred from Baseline (following study medication administration) to end of core study (i.e. end of DPC period). AEs reported after termination/completion of the core study, during the Follow-up period will be reported separately. AEs reported during the OLE period will be reported separately and together with the core study. The final safety analysis will be detailed in the Statistical Analysis Plan (SAP). The date and time of each AE occurrence will be recorded.

All AEs, whether observed by the Investigator or designee or volunteered by the patient, should be recorded individually on an AE eCRF page with the following information: the specific event or condition, whether the event was present pre-study (and if so, should be captured in the medical history eCRF page), the dates and times (using the 24 hour clock, where midnight is 00:00 and noon is 12:00) of occurrence, duration, severity, relationship to study medication, specific countermeasures, outcome, and whether considered non-serious or serious, drug-related or not. AEs will be recorded from the time a patient has signed the informed consent form (ICF) and throughout the study, including the Core study, Follow-up and OLE period. Severity of the AE will be assessed by the Investigator in accordance with the definitions below. An SAE must fulfill the requirements listed in the [Section 7.2](#).

Three definitions only should be used by the investigating physician to describe the severity of the AE ([Table 1](#)). Only one severity (the worst severity) definition should be used for each AE (e.g., "mild/moderate" is not acceptable).

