#### **6.9.2.2 OLE**

AEs will be considered treatment emergent for the purpose of reporting in the OLE if they meet any of the following criteria:

- AE onset date is after the end of treatment in the DPC period (i.e., date of onset greater than the end of treatment date in the DPC period)
- AE is ongoing, and the severity worsens during the OLE (i.e., date of severity worsening is greater than the end of treatment date in the DPC period)

All summaries will be presented by final dose group (i.e., 40, 60 or 80) and overall for the OLE set.

If the day of onset of an AE is missing, then if the month and year of an onset date are on or after the date of randomization, the following rules will be applied:

- If month/year of the onset date is on or after the month/year of the end of treatment date in the DPC period, the AE will be considered treatment emergent;
- If month/year of the onset date is equal to the month/year of the end of treatment date in the DPC period, and the end date is present, the end date will be used to determine when the AE started. If the end date is on or after the end of treatment date in the DPC period, the AE will be considered treatment emergent; otherwise, if the AE stopped before randomization, then it will not be considered treatment emergent;
- If month/year of the onset date is equal to the month/year of the end of treatment date in the DPC period, and the end date is a partial date, the AE will be considered treatment emergent;
- If, despite implementing the above conventions, the onset date of the AE cannot be placed before, on, or after the end of treatment date in the DPC period, then the event will be considered treatment emergent.

Summaries of TEAEs will be presented using the MedDRA level hierarchy (system organ class, high level group term, high level term, and preferred term) as follows:

Overall (i.e., regardless of intensity or relationship to treatment)

By intensity grade (mild, moderate, severe)

By relationship to study medication (potential relationship to study treatment or unlikely/no relationship to study treatment) according to the mapping scheme below:

Related: will include all AEs with a relationship rating of “related” or “possibly related”

Not related: will include all AEs with a relationship rating of “Not related”

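### The DPC treatment-emergent rule counts Baseline Day events before the first dose, contrary to protocol 7.1, and has no criterion for screening-onset events that worsen on blinded drug

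*SAP*

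**What the plan says.** SAP 6.9.2.1 opens the DPC window by date: "All AEs that occur after randomization (i.e., date of onset is on or after the date of randomization"). It closes the window at the last blinded dose: events "on or before the end of treatment (last dose of blinded study drug) in the DPC period will be considered Treatment Emergent Adverse Events". Protocol 8.4.8.1 carries the same rule.

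Protocol 7.1 defines the window differently at both ends. At the start, "AEs reported prior to dosing on Baseline Day will be captured and considered non-treatment emergent AEs". Overall, TEAEs are "all AEs that occurred from Baseline (following study medication administration) to end of core study (i.e. end of DPC period"). The same section requires the date and time of each AE to be recorded, and has AEs collected from consent onwards.

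On worsening, SAP 6.9.2.2 gives the OLE rule a second criterion, "AE is ongoing, and the severity worsens during the OLE", tied to a date of worsening after the end of DPC treatment. The DPC rule has no counterpart. Protocol 2.2.2 names as a safety outcome "Incidence of new or worsening adverse events of special interest (AESI"), while SAP 5.2 lists AESI incidence without that qualifier. SAP section 1 states that the SAP prevails where the two documents differ.

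**The concern.** There are two separate gaps.

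The first is at the start of the window. Randomisation and first dose both take place at the Baseline visit, and protocol 5.2.1 puts dosing late in it: "Study medication administration at the site (first dose, after the collection of blood samples for GH"). A rule based on the randomisation date cannot tell an event during blood sampling from one after the capsule, although the recorded onset time could.

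The second is worsening. Screening lasts up to 8 weeks and AEs are recorded throughout it. Suppose a headache is opened as a mild AE in screening and becomes severe on blinded drug. If the site updates the open record, the AE keeps its screening onset date and fails the DPC rule. If the site opens a new record, the AE passes. The same clinical course could be counted at one site and not at another.

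What is at stake is the accuracy of the randomised-period safety tables. New or worsening acromegaly symptoms recorded as AESIs also form part of the pre-defined withdrawal criteria (protocol 5.2.3). A symptom that contributed to a patient's rescue could therefore be absent from the TEAE tables.

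**Working it through.** The documents give no figure to reproduce, so the check applies each rule to the same set of events.

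Inputs:
- Window start: onset date on or after randomisation (SAP 6.9.2.1, protocol 8.4.8.1), or after first dose (protocol 7.1).
- Window end: last blinded dose (SAP 6.9.2.1, protocol 8.4.8.1), or end of the DPC period (protocol 7.1).
- Worsening criterion: none in the DPC rule or in protocol 7.1's TEAE sentence; present in SAP 6.9.2.2.
- Pre-dose interval on Baseline Day: five GH samples 30 minutes apart, so 4 × 30 = 120 minutes at least (protocol 5.2.1).
- Arm size: about 50 randomised 1:1, so 50 / 2 = 25 per arm (SAP 3.2).

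The study days below are illustrative. Day 0 is the day of randomisation and first dose, and week 36 is day 36 × 7 = 252.

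| Case | SAP 6.9.2.1 and protocol 8.4.8.1 | Protocol 7.1 window | Definition proposed under the fix |
|---|---|---|---|
| 1. Day 0, before first dose | TEAE | Not TEAE | Not TEAE |
| 2. Day 0, after first dose | TEAE | TEAE | TEAE |
| 3. Screening onset, unchanged | Not TEAE | Not TEAE | Not TEAE |
| 4. Screening onset, one record, worsens day 40 | Not TEAE | Not TEAE | TEAE |
| 5. Worsening entered as a new record, day 40 | TEAE | TEAE | TEAE |
| 6. Last dose day 100, onset day 150 | Not TEAE | TEAE | Depends on the end point chosen |

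Case 1 is a direct contradiction between protocol 7.1 and the rule that will be programmed. Cases 4 and 5 describe the same clinical course with different results, decided only by how it was recorded. Case 6 is a further conflict, at the end of the window. It affects patients who stop study drug early and are followed to week 36.

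Scale: one reclassified patient moves an arm's rate by 1 / 25 = 4.0 percentage points and the overall rate by 1 / 50 = 2.0 points.

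**The case against.** The strongest reply concerns worsening. Protocol 7.1 calls the worsening of a pre-existing condition an AE. Section 7.1.1 treats a shift in severity as a worsening to be recorded as an AESI. Section 5.8.1 has exacerbations of existing conditions, including acromegaly symptoms, recorded as AEs, and Appendix B sends worsened findings to the AE form. Conditions present before the study go to medical history (sections 5.1 and 5.8.2), so their later worsening is a new AE with an on-treatment onset and is counted. The instruction "Only one severity (the worst severity) definition should be used for each AE" continues by barring mixed grades; it does not order sites to merge a later shift into an earlier record. Nor does protocol 7.1's own TEAE sentence have a worsening limb, so the contradiction with 7.1 lies in the window, not in worsening.

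All of this stands, and it narrows the gap to symptoms first opened as AEs in screening, still open at baseline, and kept on the same record when they worsen. It does not close the gap. No passage tells sites which way to record such an event, and the OLE rule's reference to a date of worsening on an ongoing AE shows that the SAP itself expects single records to occur.

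A reader might go further and infer that AESI incidence on placebo is understated, because loss of control after injections stop should worsen symptoms more often there. The documents do not support that. They give no count of symptoms open at baseline and no worsening rates by arm. The AESI paragraph of SAP 6.9.2.1 does not say that its summaries are limited to TEAEs. It also counts a subject once, so a patient with any other counted AESI already contributes to the overall rate. Pre-dose events arise before any treatment difference and have no reason to favour an arm.

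**Conclusion.** The point holds as a defect of definition. The date-based start contradicts protocol 7.1 outright, and the recorded onset times would allow the correct split. The missing worsening criterion is a real but narrower gap, which depends on a recording practice that the documents leave open. The end of the window is also inconsistent.

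The consequence is modest. SAP 6.9 makes safety descriptive with no formal testing, and the primary endpoint is untouched. The number of patients affected is unknown. The only size the documents support is about 4 points per misclassified patient in an arm of about 25, assuming the planned 50 are randomised equally. No distortion of the comparison between arms has been shown. The case for change is that the two documents disagree, the SAP's own two periods use different logic without explanation, and the correction is cheap.

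**What to change.** Use one definition in SAP 6.9.2.1, protocol 8.4.8.1 and protocol 7.1:

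- A DPC TEAE is an AE with onset date and time at or after the first dose of blinded study drug, or an AE with earlier onset and a severity increase dated at or after that dose, in either case up to one stated end of window. The OLE criterion cannot be copied unchanged, because it is tied to the end of DPC treatment.
- Reconcile the end of the window: last blinded dose or end of the DPC period. The OLE rule in SAP 6.9.2.2 starts after the last blinded dose. If the DPC end moves to week 36, the OLE start must move too, or an event in a patient who stopped early and then entered the OLE would be counted in both periods.
- Re-key the partial-date rules from randomisation to first dose. Treat a Baseline Day event with missing time as emergent.
- State that AESI summaries use this definition, and restore the restriction to new or worsening events in SAP 5.2.
- Give sites one recording instruction: enter a severity increase after first dose as a new AE record with its own onset date.

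The cost is a small amount of wording, programming and eCRF-guideline work; onset times are already collected. AE and AESI counts may change slightly.

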## 3 Study Design

This will be a phase 3, randomized, double-blind, placebo-controlled, multicenter study to evaluate the safety and efficacy of octreotide capsules in acromegaly patients who previously tolerated and demonstrated biochemical control on injectable SRL treatment.

Patients meeting the pre-defined withdrawal criteria, IGF-1  $\geq 1.3 \times \text{ULN}$  AND exacerbation of acromegaly clinical signs or symptoms compared to baseline, for 2 consecutive assessments, while treated for at least two weeks with 4 capsules per day, during the DPC period, will be rescued with injectable SRL treatment used prior to Screening and will continue to be followed per protocol until week 36. At week 36, these patients will be offered to enter the OLE period and receive octreotide capsules. Patients who do not complete the full 36-week DPC period will not be eligible to enter the OLE period and will not require further follow up beyond week 36.

Patients who discontinue study medication early during the DPC period for reasons other than the pre-defined withdrawal criteria, should continue to be followed per protocol until week 36. The Sponsor recommends re-initiation of their prior injectable SRL treatment (as rescue or escape medication) upon meeting the pre-defined withdrawal criteria described above. These patients will not be eligible to enter the OLE period and will not require further follow up beyond week 36.

Patients who discontinue study medication during the OLE period, for any reason, or have completed the 36-week DPC period on study medication and are ineligible or not opting to continue into the OLE period, will revert to their prior injectable SRL treatment (prior to Screening) or other treatment as determined by their physician. These patients will be followed-up for 12 weeks after end of treatment (EOT).

Database lock for the DPC period will occur after the last patient completes the DPC period. At this timepoint, the study will be unblinded and all data from the DPC period analysed. Interim analyses of the OLE period will be conducted periodically, after completion of the DPC period. Data collected post DPC period (week 36) in patients not entering the OLE period and those who entered the OLE period will be included in the OLE database.

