### 4.4 Open Label Extension Sets

For the OLE phase, several different analysis sets will be defined.

1. The open label extension (OLE) set will consist of all patients enrolled into the OLE phase of the study who receive at least one dose of open label study drug.
2. Octreotide capsule patients from the DPC period who enrolled into the OLE phase and received at least one dose of open label study drug (OLE-OCT)
3. Octreotide capsule patients from the DPC period, who were classified as treatment responders based on the primary endpoint, at the end of the DPC period, and who enrolled into the OLE phase and received at least one dose of open label study drug (OLE-OCT-RESP).

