## 6.9 Safety Analyses

All safety analyses for data collected during the DPC period will be presented using the safety set. All safety analyses for data collected during the OLE will be presented using the OLE set (summaries by treatment group will be based on the treatment group in the DPC period). Safety analyses for the DPC period will only use data collected during the DPC period, and will exclude any safety data that was collected after a subject had discontinued study drug. Safety analyses for the OLE will include data collected during the OLE. No formal hypothesis testing will be conducted. Data will be summarized using appropriate descriptive statistics. Missing data will be maintained as missing, unless indicated.

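### Fully dated adverse events that start after the last blinded dose have no planned table in patients who never enter the open-label extension, and the protocol gives two conflicting windows for them

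*SAP*

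**What the plan says.** **SAP, DPC period.** Section 6.9.2.1 says that events with onset from randomization onwards but "on or before the end of treatment (last dose of blinded study drug) in the DPC period will be considered Treatment Emergent Adverse Events". No days are added after the last dose. Section 6.9 says that DPC safety analyses "will exclude any safety data that was collected after a subject had discontinued study drug".

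**SAP, extension.** Section 6.9.2.2 opens a second window, whose first criterion is that "AE onset date is after the end of treatment in the DPC period". Its tables have a restricted population: "All summaries will be presented by final dose group (i.e., 40, 60 or 80) and overall for the OLE set". Section 4.4 defines that set as "all patients enrolled into the OLE phase of the study who receive at least one dose of open label study drug". Section 3 says that "Data collected post DPC period (week 36) in patients not entering the OLE period" are held in the extension database along with the data of those who do enter.

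**Protocol.** Section 7.1 counts as TEAEs all "AEs that occurred from Baseline (following study medication administration) to end of core study (i.e. end of DPC period". It adds that "AEs reported after termination/completion of the core study, during the Follow-up period will be reported separately", and leaves the details of the final safety analysis to the SAP. Section 8.4.8.1, the protocol's own analysis section, has the same last-dose window as the SAP.

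**Collection.** Protocol 5.8.1 has adverse events recorded throughout, follow-up included. Protocol 4.6.1 keeps early stoppers on scheduled visits to Week 36; those who stopped for reasons other than the withdrawal criteria cannot enter the extension. Protocol 5.5 follows completers who do not enter it for 12 weeks.

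**The concern.** Comparing the safety of capsules with placebo is a stated secondary objective (Protocol 2.1, SAP 2.2). The design keeps collecting adverse events after capsules stop, but the analysis rules give some of those events no place. Whether an off-drug event is tabulated depends on why the patient stopped and on whether the patient later took open-label drug. If reasons for stopping differ between the arms, which is plausible when placebo patients are withdrawn from effective treatment, the handling of off-drug events differs between the arms too.

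At stake are late events after capsules and events while coming off treatment. A reader of the DPC tables could not tell how many there were or in which arm.

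**Working it through.** The plan states no figure on this point, so the check is to apply its rules to test cases and then count the time that no table covers.

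**Rules.** SAP: an event is a DPC TEAE if onset is on or before the last blinded dose. It is an extension TEAE if onset is later and the patient is in the OLE set. Protocol 7.1: an event is a DPC TEAE if onset is by Week 36 (day 36 × 7 = 252), and is reported separately if it falls in the follow-up after that.

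| Patient | Last blinded dose | Onset | SAP | Protocol 7.1 |
|---|---|---|---|---|
| Early stopper, never in OLE | day 84 | day 85 | no table | DPC TEAE |
| Early stopper, never in OLE | day 84 | day 200 | no table | DPC TEAE |
| Rescued, later enters OLE | day 84 | day 200 | extension TEAE | DPC TEAE |
| Completer, not in OLE | day 252 | day 270 | no table | separate report |
| Completer | day 252 | day 240 | DPC TEAE | DPC TEAE |

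The third row is a related fault. The event occurs before any open-label capsule, yet it is tabulated under the patient's final extension dose. A rescued patient who does not go on to the extension would be in the position of the first two rows.

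**Is the gap covered elsewhere?** SAP 6.9.3 to 6.9.6 send off-drug laboratory, vital-sign, ECG and ultrasound data to listings; the adverse-event sections have no such sentence. The AESI (adverse events of special interest) summaries in 6.9.2.1 are not worded as treatment emergent, but the exclusion in 6.9 still removes off-drug AESIs. Sections 6.9 to 6.9.6 show no redaction. One leak exists: under 6.9.2.1, an event with a missing onset day counts as treatment emergent if its month is on or after randomization, with no check against the last dose. A partly dated off-drug event could thus be counted while a fully dated one is not.

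**Time without a table, per patient.** For an early stopper who never enters the extension, this is at most 36 − stopping week:

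- Week 8: 36 − 8 = 28 weeks; 28/36 = 78%
- Week 20: 36 − 20 = 16 weeks; 16/36 = 44%
- Week 32: 36 − 32 = 4 weeks; 4/36 = 11%

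For a completer not entering the extension it is the 12-week follow-up, which consists of one clinic visit and one telephone call.

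**Illustration on assumed rates.** Planned DPC time is 50 × 36 = 1,800 person-weeks. Suppose that a share d of the 50 patients stops early and never enters the extension, at mean week s. The uncovered time is 50 × d × (36 − s):

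- Low end, d = 10%, s = 24: 50 × 0.10 × 12 = 60 person-weeks (3.3%)
- High end, d = 40%, s = 8: 50 × 0.40 × 28 = 560 person-weeks (31.1%)

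If 5% to 20% of the 50 complete but do not enter the extension, a further 50 × 0.05 × 12 = 30 to 50 × 0.20 × 12 = 120 person-weeks are uncovered. These rates are assumptions, and full attendance is assumed as well.

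**The case against.** The strongest reply is that an on-treatment window is a legitimate primary choice, that both analysis sections (Protocol 8.4.8.1 and SAP 6.9.2.1) use it, and that Protocol 7.1 defers to the SAP. All of that stands. It means that the protocol disagrees with itself, so a reader should not infer that the protocol as a whole counts these events. It does not supply a table for them.

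For completers' follow-up, the SAP is silent and contradicts nothing. Its precedence clause (SAP 1) covers discrepancies only, so the Protocol 7.1 commitment to separate reporting survives. That stands too, but no output is specified to meet it.

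A reader might infer that the patients who tolerate capsules worst disappear from the safety comparison. The documents do not support this. An event that starts on drug and leads to stopping is in the TEAE table and in the discontinuation table. Worsening that meets the withdrawal criteria arises while the patient takes blinded capsules, so it is also counted. Serious events are still reported individually under Protocol 7.4.

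A reader might also apply a general stopping rate to 50 patients and read off the number affected. That would include patients rescued under the withdrawal criteria, who may enter the extension and then appear in its tables. The weeks per patient are likewise ceilings, because Protocol 4.7 foresees loss to follow-up and withdrawn consent.

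**Conclusion.** The point holds in a limited form and should be corrected. The gap concerns fully dated events with onset after the last blinded dose, in early stoppers barred from the extension and in completers who do not enter it. It lies in the planned summaries; collection and serious-event reporting are not in question. For the early stoppers, Protocol 7.1 conflicts with Protocol 8.4.8.1 and the SAP, and the SAP's narrower window would be applied. For the completers, a promised report has no specification.

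The number of patients affected cannot be derived from the documents. Only the per-patient ceilings (36 minus the stopping week, or 12 weeks of follow-up) follow from the text. The person-week ranges rest on assumed rates and serve only to show scale.

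**What to change.** 1. Reconcile Protocol 7.1, Protocol 8.4.8.1, SAP 6.9 and SAP 6.9.2.1 on the window, and state how the missing-day rule treats onsets after the last dose.
2. Keep the on-treatment TEAE table as primary.
3. Add to SAP 6.9.2.1 a table and a listing of adverse events, serious events, deaths and AESIs with onset after the last blinded dose. Run it to Week 36 for early stoppers and to the end of the 12-week follow-up for completers not entering the extension. Split it at the start of any injected somatostatin ligand (SRL).
4. Add a table of serious events and deaths over the whole DPC period, regardless of treatment.
5. Present both tables by randomized arm. The as-treated rule in SAP 4.3 assigns to the octreotide group anyone who received octreotide in the DPC period. Read literally, it could move placebo patients rescued with injected octreotide into that group.
6. State that off-drug events before the extension, in rescued patients who later enter it, belong in the new table and not in the extension TEAE tables. This avoids double counting and attribution to a dose not yet taken.

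The cost is SAP and protocol wording and a few outputs from data already collected. Some events in the new tables will occur on injected SRL; the split in item 3 makes those visible in the post-treatment table.
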